10.2.1.1 COVID-19 related considerations

To assess the impact of COVID-19 mass vaccination on TEAEs, a sensitivity analysis will present all TEAEs excluding TEAEs assessed as exclusively related to COVID-19 vaccine by the investigator. TEAEs recorded as related to both study medication and COVID-19 vaccination should not be excluded. A complementary table and listing of TEAEs related to COVID-19 vaccine will be presented.

Another sensitivity analysis will present all TEAEs excluding TEAEs with start date on or up to 5 days after date of COVID-19 vaccine. Note that study participants may receive more than one administration of COVID-19 vaccine. A complementary table and listing of TEAEs with start date on or up to 5 days after date of COVID-19 vaccine will also be presented.

10.2.2 AE summaries

The following summaries will be provided by treatment group for the Initial Treatment Period, and the Initial and Maintenance Treatment Period combined based on the SS, and AMS respectively. In addition, all summaries of TEAEs based on “100 subject years” will include EAIR (with 95% confidence interval) and EAER. For AEs that emerged after 112 days but still within the 140 days window, those AEs would be classified as TEAE. These AEs will be excluded from the outputs based on the Initial Period but included in the AE summaries for Initial and Maintenance Treatment Period.

- Incidence of TEAEs – Overview
- Incidence of TEAEs per 100 subject years by SOC, HLT, and PT
- Incidence of Serious TEAEs per 100 subject years by SOC, HLT, and PT
- Incidence of TEAEs Leading to Study Participant Discontinuation per 100 subject years by SOC, HLT, and PT
- Incidence of TEAEs Leading to Death by SOC, HLT, and PT
- Incidence of TEAEs by Maximum Relationship by SOC, HLT, and PT
- Incidence of Serious TEAEs by Relationship SOC, HLT, and PT – Note: For EudraCT reporting purposes
- Incidence of Related Serious TEAE by SOC, HLT, and PT
- Incidence of Severe TEAE per 100 subject years by SOC, HLT, and PT

- Incidence of TEAEs Leading to Death by Relationship by SOC, HLT, and PT – Note: For EudraCT reporting purposes
- Incidence of TEAEs by Maximum Severity, SOC, HLT, and PT
- Incidence of TEAEs by decreasing frequency of PT
- Incidence of TEAEs Above Reporting Threshold of 5% by SOC and PT
- Incidence of Non-Serious TEAEs by SOC, HLT, and PT
- Incidence of Non-Serious TEAEs by Maximum Relationship SOC, HLT, and PT
- Incidence of Non-Serious TEAEs Above Reporting Threshold of 5% by SOC and PT
- Incidence of Non-Serious TEAEs Above Reporting Threshold of 5% by Relationship SOC and PT
- Incidence of Related TEAEs per 100 subject years by SOC, HLT, and PT
- Incidence of Related TEAEs Above Reporting Threshold of 5% by SOC and PT
- Incidence of TEAEs – Suspected and Confirmed COVID-19 cases by SOC, HLT and PT
- Incidence of TEAEs Excluding TEAEs Exclusively Related to COVID-19 Vaccine by SOC, HLT, and PT
- Incidence of TEAEs Exclusively Related to COVID-19 Vaccine by SOC, HLT, and PT
- Incidence of COVID-19 Vaccine Interval Censored TEAEs by SOC, HLT, and PT
- Incidence of COVID-19 Vaccine Interval TEAEs by SOC, HLT, and PT

Suspected and confirmed COVID-19 cases will be identified with the preferred terms “Corona virus infection” or “Corona virus test positive”.

The following subset of tables will also be presented for the Maintenance Treatment Period using the MS:

- Incidence of TEAEs – Overview
- Incidence of TEAEs per 100 subject years by SOC, HLT, and PT
- Incidence of Serious TEAEs per 100 subject years by SOC, HLT, and PT
- Incidence of TEAEs Leading to Discontinuation per 100 subject years by SOC, HLT, and PT
- Incidence of TEAEs Leading to Death by SOC, HLT, and PT

The following tables will be presented for the Initial Treatment Period:

- Incidence of TEAEs Above Reporting Threshold of 5% with Risk Differences by SOC and PT
- Incidence of Serious TEAEs and Risk Differences by SOC and PT

The following table will be presented for the combined Initial and Maintenance Treatment Period. This summary will include only AEs that occur while a participant is on bimekizumab.

Any AEs in the Initial Treatment Period that begin while a participant is on placebo will be excluded.

- Incidence of TEAEs per 100 subject years by SOC, HLT, and PT and by Time of Onset Relative to Anti-bimekizumab Antibody Status. This will include columns for the following:
 - TEAEs starting before the first ADAb positive result (includes ADAb categories 2 and 5) where TEAEs have occurred before the following events: a) the first positive ADAb result for subjects in category 2 and b) the first post-Baseline boosted ADAb titer result for subjects with titer results and the first post-Baseline positive ADAb result for subjects with positive ADAb at Baseline with no other samples with titer available for subjects in category 5
 - TEAEs starting on the same date or after the first ADAb positive result (includes ADAb Categories 2, 3, 4, 5 and 6) where TEAEs have occurred on or after the following events: a) the first positive ADAb results for subjects in categories 2, 3, 4 and 6, and b) the first post-Baseline boosted ADAb titer result for subjects with titer results and the first post-Baseline positive ADAb result for subjects with positive ADAb at Baseline with no other samples with titer available for subjects in category 5
 - TEAEs for subjects who are ADAb negative at all timepoints (includes ADAb Category 1)

The tables with risk differences will also be accompanied by figures (dot plots) which show the incidence of the adverse events and corresponding 95% risk difference confidence intervals. These will be ordered by descending order of risk difference (bimekizumab vs placebo).

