- **Pre ADA_b positive – treatment-emergent reduced ADA_b (Category 3):** Includes study participants who are ADA_b positive at Baseline, and ADA_b negative at all sampling points post-Baseline during the period of interest.
- **Pre ADA_b positive – treatment-emergent unaffected ADA_b positive (Category 4):** Includes study participants who are ADA_b positive at Baseline and are ADA_b positive at any sampling point post-Baseline during the period of interest with titer values of the same magnitude as Baseline (ie, less than a predefined fold difference from the Baseline titer).
 - For this analysis, this is set at an increase of less than the validated Minimum Significant Ratio (MSR) of 2.07-fold from Baseline.
- **Pre ADA_b positive – treatment-emergent ADA_b boosted positive (Category 5):** Includes study participants who ADA_b positive at Baseline and are ADA_b positive at any sampling point post-Baseline during the period of interest with increased titer values compared to Baseline (equal to or greater than a predefined fold difference increase from Baseline titer which will be defined within the validation of the assay).
 - For this analysis, this is set at an increase equal to or greater than the validated MSR of 2.07-fold from Baseline.
 - Note: for any study participant who is ADA_b positive at Baseline and ADA_b positive at a post-Baseline time point during the period of interest, but for whom titers are not available to determine treatment unaffected or treatment boosted status, the study participant will be considered as treatment boosted, assuming no other samples are available.
- **ADA_b Inconclusive (Category 6):** Includes study participants who have an ADA_b positive Baseline (pre-treatment) sample and some post-Baseline samples during the period of interest are missing or inconclusive, while other post-Baseline samples are ADA_b negative.
- **Total treatment-emergent ADA_b positivity (Category 7 [Categories 2 and 5 combined]):** Includes study participants who are pre ADA_b negative – treatment-emergent ADA_b positive (Category 2) and pre ADA_b positive – treatment boosted ADA_b positive (Category 5).
- **Total prevalence of pre- ADA_b positivity (Category 8 [Categories 3, 4, 5 and 6 combined]):** Study participants that are tested ADA_b positive at Baseline.

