- **Missing:** Includes study participants who are ADA_b negative, missing, or inconclusive at Baseline with some post-Baseline samples as missing or inconclusive, and other samples as ADA_b negative.

For purposes of efficacy subgroup analyses based on anti-bimekizumab antibody status, the following categories can also be used:

- ADA_b positive – This is defined as study participants who are anti-bimekizumab antibody positive on at least 2 time points while on treatment (ie, excluding Baseline, excluding SFU).
- ADA_b negative – Study participants for who either:

- All samples (including Baseline) are ADAb negative and there are no missing or inconclusive samples
- Only 1 sample is ADAb positive and all other samples (including Baseline) are ADAb negative or missing or inconclusive
- Only 1 sample is missing or inconclusive and the remaining ADAb samples are negative.
- ADAb missing - Defined as study participants who do not fulfil the criteria for one of the 2 groups listed above.

The rationale for requiring at least 2 time points in which ADAb levels are above the specified cut point is to exclude those study participants who have only one occurrence of ADAb levels during the course of treatment. Including such study participants would increase the number of ADAb positive study participants with potentially no impact on efficacy.

In the case that a sample is collected 1 or more days following the scheduled visit date in which the drug was administered, the ADAb results for that sample will be associated with the scheduled visit and summarized accordingly. Such samples will also be considered when ADAb results are summarized over a given study period.

Analysis

Immunogenicity will be assessed through summary tables and figures, and listing of individual results by participants. All analyses will be run on the AMS, unless specified otherwise.

- Summary of ADAb status overall and by each visit separated by treatment group
- Summary of the time-point of the first occurrence of ADAb positivity during the treatment period by treatment group. A plot of the titer by time to first ADAb positivity will be prepared.
- All individual participant-level ADAb results will be listed.
- The number and percentage of participants in each of the 8 ADAb categories during the treatment period by treatment group.

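### The table of TEAEs by antibody onset uses two different definitions of first positivity for participants who are antibody positive at Baseline, and gives the Missing class no column

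*SAP*

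**What the plan says.** Section 10.2.2 specifies, for the combined Initial and Maintenance Treatment Period, TEAE incidence per 100 subject years by time of onset relative to ADAb status. Only events occurring on bimekizumab count. Three columns are listed:

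1. "TEAEs starting before the first ADAb positive result (includes ADAb categories 2 and 5".
2. "TEAEs starting on the same date or after the first ADAb positive result (includes ADAb Categories 2, 3, 4, 5 and 6".
3. "TEAEs for subjects who are ADAb negative at all timepoints (includes ADAb Category 1".

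Columns 1 and 2 also name the event at which each category is cut. For Category 5 it is "the first post-Baseline boosted ADAb titer result for subjects with titer results", with the first post-Baseline positive result as fallback when titers are unavailable. In column 2 the other categories are cut at "the first positive ADAb results for subjects in categories 2, 3, 4 and 6".

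Section 9.3.2 defines the categories. Category 5 is described as follows: "Includes study participants who ADA_b positive at Baseline and are ADA_b positive at any sampling point post-Baseline", with a titer rise set at "an increase equal to or greater than the validated MSR of 2.07-fold from Baseline". Categories 3, 4 and 6 are likewise positive at Baseline, and Category 8 pools all four. Category 7, total treatment-emergent positivity, is Categories 2 and 5. A further class, Missing, stands outside the numbered categories: "Includes study participants who are ADA_b negative, missing, or inconclusive at Baseline with some post-Baseline samples as missing or inconclusive", with the other samples negative. Section 9.3.2 also names the safety subgroups in terms of the first ADAb positive result, without qualification, and refers to Section 10.2.2 for detail.

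**The concern.** A reader of the finished table will take the before column as time without ADAb and the on-or-after column as time following ADAb formation. For Category 5 the first reading is false, because these participants carried ADAb before their first bimekizumab dose. For Categories 3, 4 and 6 the second is not what happened, because their ADAb pre-dated treatment and was not boosted by it.

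This is the only AE table by ADAb status that the SAP specifies. A defined class with no place in it also means that the columns do not add up to the bimekizumab-treated participants, and nothing in the plan tells the reader how many are absent or how much time at risk they carry.

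**Working it through.** The plan states no figure to reproduce. The check maps each class of Section 9.3.2 onto the column rules of Section 10.2.2.

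| Class (9.3.2) | ADAb at Baseline | Cut event (10.2.2) | Column(s) | Fits the column label? |
|---|---|---|---|---|
| 1 | Negative, or missing/inconclusive with all later samples negative | None | 3 | Broadly; one missing or inconclusive post-Baseline sample is tolerated if Baseline is negative |
| 2 | Negative or missing | First positive result | 1, then 2 | Yes |
| 3 | Positive | First positive result, i.e. Baseline | 2 | Yes, literally |
| 4 | Positive | Baseline | 2 | Yes, literally |
| 5 | Positive | First boosted titer | 1, then 2 | No: column 1 events follow the first positive result |
| 6 | Positive | Baseline | 2 | Yes, literally |
| Missing | Negative, missing or inconclusive | None given | None | No column |

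**Does any single definition give this allocation?**

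- Literal first positivity: Category 2 is split, and Categories 3, 4, 5 and 6 all fall wholly in column 2. The plan departs from this for Category 5.
- Treatment-emergent (new or boosted) positivity: Category 2 is split at its first positive result and Category 5 at its boost. Categories 3, 4 and 6 never reach the event, so they cannot be on or after it. The plan departs from this for Categories 3, 4 and 6.

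Neither definition reproduces the plan's columns.

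**Example.** Two participants are ADAb positive at Baseline, and each has a TEAE at Week 2. In one, the titer later rises by at least 2.07-fold (Category 5), so the Week 2 event is counted before the first positive result. In the other, positivity persists without such a rise (Category 4), so the same event is counted on or after it. Both were equally positive when the event began.

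**Who falls into Missing?** Section 9.3.2 schedules eight post-Baseline samples up to Week 48 (Weeks 4, 8, 12, 16, 20, 24, 36 and 48). A non-positive sample is inconclusive when the bimekizumab concentration exceeds the assay's drug tolerance limit. Category 1 absorbs one missing or inconclusive post-Baseline sample in a Baseline-negative participant. With two such samples and no positive, that participant is in Missing. The class can therefore arise from drug exposure as well as from missed visits.

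**The case against.** The strongest reply is that the allocation is explicit and deliberate. Section 10.2.2 names the cut event for each category, so a programmer can place the events of Categories 1 to 6 without guessing. The two categories split before and after are exactly those in Category 7, each cut at its treatment-emergent event. Categories 3, 4 and 6 fit the literal wording of column 2, including Category 3, because the column concerns time since the first positive result and not current status. All of this stands. It does not remove the mismatch between the Category 5 rule and its label, or the use of a different definition for the other Baseline-positive categories in the same column.

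It is also true that later samples decide the column for early events elsewhere. They separate Category 1 from Category 2, and the repair below keeps that feature. Sorting by later results is therefore not in itself the defect.

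On Missing, the wording that introduces the columns does not forbid a further one, and these participants remain in the main TEAE tables on the Active Medication Set. Even so, no column is specified for them, and followed as written the table omits them.

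A reader might go further and infer that the table could hide or create a hypersensitivity signal, or that a large share of the on-or-after time is misplaced. The SAP supports neither. Section 10.2.3.7 gives anaphylaxis, hypersensitivity, serious hypersensitivity and injection site reactions their own tables regardless of ADAb status. Most Baseline-positive categories fit the literal label, and no prevalences are given from which a share could be calculated.

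**Conclusion.** Two defects are established from the text alone. First, the stated rule counts Category 5 TEAEs before boosting under a label that cannot apply to them, while Categories 3, 4 and 6, equally positive at Baseline, are cut at Baseline; the columns thus mix two definitions. Second, the Missing class is defined in Section 9.3.2 but has no column in Section 10.2.2, so its events and time at risk are left out.

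The size is unknown. It depends on how many participants are Baseline positive, how many of those boost and when, and how many end up in Missing; the SAP reports none of these. The consequence is confined to the interpretation of one descriptive safety table. No hypothesis test, alpha allocation or power calculation is touched. It is a minor point, but more than a matter of wording, because a programmed rule and an omitted class are involved.

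**What to change.** Use one definition throughout the table:

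- Relabel columns 1 and 2 as before, and on or after, first treatment-emergent (new or boosted) ADAb positivity, and limit them to Categories 2 and 5, the plan's own Category 7. The existing cut events for these two categories can stay.
- Move Categories 3, 4 and 6 to a separate column for pre-existing ADAb without boosting.
- Keep the Category 1 column and add a Missing column with its events and time at risk, so that every bimekizumab-treated participant appears.
- Align the safety subgroup names at the end of Section 9.3.2 with these labels.

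The cost is SAP text and a table shell, with no new data. The downside is a wider descriptive table in which some columns may be small.

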10.2.3 Other Safety topics of interest

The following are AEs considered to be other safety topics of interest that require special statistical analyses. Along with the tables described, there will be a table which displays the risk difference and 95% confidence intervals for each of the topics of interest in the Initial Treatment Period. A corresponding figure (with dot plots) will be prepared.

A by-participant listing of all AEs of safety topics of interest will be presented by type of safety topics of interest.

10.2.3.1 Infections (serious, opportunistic, fungal and TB)

- **Incidence of Serious Infection TEAEs per 100 subject years by SOC, HLT and PT**

Serious infections will be identified based on MedDRA classification (SOC “Infections and infestations”) using the “Any SAE” table. A separate table does not need to be produced to summarize these events.

- **Incidence of Fungal Infection TEAEs per 100 subject years by SOC, HLT and PT**

Fungal infections will be summarized in a stand-alone table. The table will include all TEAEs (serious and non-serious) that code into the High Level Group Term (HLGT) “Fungal infectious disorders”

- **Incidence of Opportunistic Infection TEAEs per 100 subject years by SOC, HLT and PT**

Opportunistic infections (including tuberculosis) will be summarized in a stand-alone table. The table will include all TEAEs identified using UCB-defined search criteria .

The following steps will be followed for identifying and reviewing opportunistic infections:

Identification Process

The steps below outline 2 ways in which opportunistic infections (or potential opportunistic infections) can be identified:

Step 1: Refer to column B of the spreadsheet, which identifies the PTs to be classified as opportunistic infections using either a single 'x' or a double 'xx'.

- All TEAEs that code to a PT flagged with a single 'x' need to also be serious to be considered an opportunistic infection.
- All TEAEs that code to a PT flagged with a double 'xx' are considered to be an opportunistic infection, regardless of seriousness.

Step 2: Refer to column C of the spreadsheet, which identifies the PTs that need to be evaluated on a case-by-case basis by the study physician to determine whether or not it is an opportunistic infection. If column C has a single 'x', then the corresponding preferred term will be flagged for case-by-case review by the study physician.

Review Process

Opportunistic infections for a given study will be reviewed on the following occasions:

- At quarterly Infectious Disease Committee (IDC) Meetings, listings will be produced for each study (see details below) and reviewed by the corresponding study physician ahead of the IDC Meeting. These listings will be posted as part of the broader Safety Signal Detection (SSD) deliverable to a folder named for the given quarter (eg, 2018Q4) on the SharePoint. They will be based on the same data cut as the one used for SSD and will be delivered at the same time as the SSD outputs. The IDC will then agree on the final adjudication for each potential opportunistic infection.
- For each study, a final listing for opportunistic infections (in the format described below) will be produced and agreed upon between the study physician and the IDC prior to finalizing the database.

In each of the circumstances described above, the study programming team will produce an Excel listing that will be provided to the project lead statistician, project lead programmer, and to the study physician (who will subsequently provide it to the IDC). The Excel listing will contain the following columns (using the descriptions below as the column headings in the Excel listing):

- Study ID
- Unique Participant ID
- AE Term (Verbatim)
- AE Preferred Term
- AE System Organ Class
- AE High Level Term

- AE Low Level Term
- Date of Onset
- Outcome of Adverse Event
- Date of Outcome
- TEAE Flag
- Serious Adverse Event?
- Relationship to Study Medication
- Intensity
- Action Taken with IMP
- Opportunistic Infection – Automatic
- Opportunistic Infection – Manual Review
- Flag
- Data Cut Date
- Opportunistic Infection – Final Adjudication

Note the following about the final 5 variables in this listing:

- *Opportunistic Infection – Automatic*: This is flagged as “Y” if the criteria for automatic selection as described in “Step 1” of the identification process are met.
- *Opportunistic Infection – Manual Review*: This is flagged as “Y” if the criteria for case-by-case selection as described in “Step 2” of the identification process are met.
- *Flag* – This has a value of either “NEW” or “OLD”. It is marked as “NEW” if the event is appearing for the first time in that run of the listing. Otherwise, if it has appeared previously, it is marked as “OLD”. Unique records are determined by USUBJID AESPID for purposes of identifying whether an event has been modified from a previous run.
- *Date* – Only for cases where Flag is “NEW”, this field will be populated with the data cut date for that particular run of the listing.
- *Opportunistic Infection – Final Adjudication* – For new events, this is always left blank by the programmers. It will be completed by the study physician/IDC for every event that appears in the listing. For events adjudicated as opportunistic, the field will be populated with a “Y”.

Following each review by the study physician and IDC, the Opportunistic Infection – Final Adjudication column will be completed (as described above), and the spreadsheets for each study will be returned to the study programming team via e-mail (coordinated by the IDC secretary). Then, for subsequent runs of the listing, the study programming teams will incorporate adjudications from previous runs.

